3.2. Study Endpoints

3.2.1. Primary Endpoints

Safety

The primary safety endpoints are:

- 1) The incidence of serum potassium >6.5 mEq/L
- 2) The incidence of serious hypotension defined as hypotension requiring hospitalization or treatment in an emergency room and not attributable to overt sepsis, acute myocardial infarction, or other cardiovascular event (e.g. aortic dissection).

Tolerability

Tolerability will be assessed on the basis of whether participants can continue the assigned dose throughout the entire treatment period. Any reduction in dose of study medication will be considered a failure of primary tolerability.

Efficacy

The primary efficacy parameters will be measured between baseline and 36 weeks: Change in mitral annular E' velocity will be measured using Tissue Doppler Index (TDI) echocardiography of the left ventricle as a measure of diastolic function and as surrogate measure of left ventricular fibrosis.

E' has been chosen to be the primary echocardiographic endpoint because the intra-observer coefficient of variation is low⁷¹ and multiple studies demonstrate a high correlation with myocardial fibrosis⁷²⁻⁷⁴, a primary biologic endpoint of interest. E', for example, parallels the accumulation of myocardial collagen and fibrosis in the senescence prone mouse⁷⁵, and correlates with endomyocardial fibrosis after human cardiac transplant⁷⁶ as well as the presence of late gadolinium enhancement⁷⁷ – a highly-validated measure of myocardial scar – across multiple disease states. Furthermore, abnormalities in TDI have been strongly linked to mortality in multiple disease states⁷⁸⁻⁸⁰ demonstrating that TDI is a clinically relevant measure. In addition, ESRD-specific studies show that E' is highly correlated with LV mass and other indices of diastolic function, and that changes in E' predict mortality^{34, 81}.

In contrast to other echocardiographic measures, E' (or the ratio of E/E') is minimally affected by intravascular volume status⁸²⁻⁸⁴ – a critical consideration in ESRD where volume status can vary widely. The adjunctive information on diastolic and systolic function and filling pressures generated by echocardiography provide additional advantages to the use of TDI while the measurement of strain rate and strain may allow detection of subtle changes in myocardial function due to fibrotic processes⁸⁵. Finally, these measures are known to respond to therapeutic interventions that exert anti-fibrotic effects⁸⁶. Alternative approaches for assessing fibrosis include myocardial biopsy which is considered the gold standard, and cardiac magnetic resonance imaging with gadolinium. However, both of these have risks of serious complications and thus are not suitable for a research study.

Feasibility

An objective of this study is to assess the feasibility of conducting a full-scale mortality-powered trial. Feasibility will be assessed based on recruitment, dropout and loss to follow-up rates.

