NIDDK	National Institute of Diabetes and Digestive and Kidney Diseases
OHRP	Office of Human Research Protections
PET	positron emission tomography
PHI	protected health information
PICP	procollagen type I carboxy-terminal peptide
PTH	parathyroid hormone
QD	daily
RCT	randomized controlled trial
SAE	serious adverse event
SAP	statistical analysis plan
SBP	systolic blood pressure
SPL	spironolactone
TDI	tissue Doppler index
UAE	unanticipated adverse event

Study Summary

Title	Safety and Cardiovascular Efficacy of Spironolactone in Dialysis-Dependent ESRD Trial
Short Title	SPin-D Trial
NCT Identifier	NCT02285920
Phase	Phase II
Methodology	Randomized, double-blind, placebo-controlled 4-arm
Study Duration	2 years
Study Center(s)	Brigham and Women's Hospital George Washington University University of Washington Vanderbilt University / Nashville VA Medical Center University of Pennsylvania (Data Coordinating Center)
Objectives	
 • To generate pilot data on the safety and tolerability of spironolactone (SPL) in patients with dialysis-dependent ESRD. • To generate pilot estimates of the effect of SPL compared with placebo on cardiovascular efficacy parameters in patients with dialysis-dependent ESRD.
Number of Participants	125
Diagnosis and Main Inclusion Criteria	Dialysis-dependent ESRD
Study Product, Dose, Route, Regimen	Spironolactone 12.5, 25, or 50 mg, orally daily
Duration of administration	36 weeks
Reference therapy	Placebo
Major Outcomes	
 • Safety: hyperkalemia, hypotension • Tolerability: treatment adherence • Efficacy: change in mitral annular E' velocity • Feasibility: recruitment
Statistical Methodology	
Mixed effects linear regression models will be used to assess the direction and time averaged magnitude of change in efficacy parameters, with and without controlling for baseline covariates, to compare the effects of therapy.
 
These mixed effects models will also be utilized to investigate the potential shift in overall potassium levels. The incidence of safety events, especially serious hyperkalemia, in treatment and placebo groups will be compared with Chi-square test or Fisher's exact test.

CONFIDENTIAL

Do not disclose or use except as authorized by the Hemodialysis Novel Therapies Consortium.

1. Introduction

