2.1. Primary Objectives

Safety

- To evaluate the safety of chronic spironolactone therapy in individuals with ESRD on HD.
 - Safety events will include the following:
 - Potassium level >6.5 mEq/L
 - Serious hypotension is defined as hypotension requiring hospitalization or treatment in an emergency room and not attributable to overt sepsis, acute myocardial infarction, or other cardiovascular event (e.g. aortic dissection)
 - Serious hyperkalemia defined as hyperkalemia requiring hospitalization, emergency/unscheduled dialysis, or emergency/unscheduled resin therapy
 - The combined incidence of potassium level >6.5 mEq/L or serious hyperkalemia defined as hyperkalemia requiring hospitalization, emergency/unscheduled dialysis, or emergency/unscheduled resin therapy
 - Treatment-emergent events defined as the combined incidence of death, myocardial infarction, stroke, hospitalizations, potassium level >6.5 mEq/L, serious hyperkalemia defined as hyperkalemia requiring hospitalization, emergency/unscheduled dialysis, or emergency/unscheduled resin therapy, and serious hypotension defined as hypotension requiring hospitalization or treatment in an emergency room and not attributable to overt sepsis, acute myocardial infarction, or other cardiovascular event
 - The individual components of the treatment-emergent endpoint
 - Cardiovascular death
 - Hyperkalemia requiring adjustment in dialysate potassium concentration, or discontinuation of study medication
 - Proportion of dialysis sessions utilizing 1 mEq/L potassium dialysis solution bath
 - Within-patient variability in serum potassium concentration
 - Symptomatic inter- or intra-dialytic hypotension

Tolerability

- To evaluate the tolerability of chronic spironolactone therapy in individuals with ESRD treated with hemodialysis
 - Tolerability events will include reduction in dose of study medication during the course of the treatment period or discontinuation of study drug

Efficacy

- To test the hypothesis that chronic blockade of aldosterone with SPL improves diastolic function in individuals with ESRD on HD. The change in E' on TDI echocardiography of the left ventricle from baseline to end of study will be used in the primary endpoint assessment of diastolic function.

Feasibility

- To assess feasibility of conducting a full-scale mortality-powered trial.
 - Feasibility will be assessed based on recruitment rate and dropout rates.

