5.4. Preparation and Administration of Study Drug and Maintenance of Blind

Study drug and matching placebo will be prepared by the University of Pennsylvania Investigational Drug Service (IDS) which will be the Central Pharmacy for this study. Study drug kits will contain 2-week supplies during the dose escalation phase, a 6-week supply for weeks 6-12, and 12-week supplies for weeks 13-24 and weeks 25-36.

Study drug will be prepared using gelatin encapsulation or equivalent methods such that all study drug, regardless of type (SPL or placebo) and dose are identical in appearance. During encapsulation, SPL tablets will remain intact and will not be altered. All dose levels will be administered as a single capsule. IDS personnel will have access to the randomization scheme and code in order to prepare study drug kits containing the correct dose of SPL or placebo. IDS personnel responsible for preparation of study drug will not have access to study data or results and will not participate in analyses of study data or publications. Randomized treatment assignments and the dosages provided in study drug kits will not be known by the Clinical Center research teams or the Clinical Center Research Pharmacy staff. Only the Investigational Drug Service personnel and the database programmer at the DCC will be unblinded.

During the 6-week dose escalation phase, a study drug request form signed by a Clinical Center investigator will be entered into the data management system at each 2-week interval to request the next supply of study drug. Unless there is a contraindication to a dose increase (e.g. hypotension or hyperkalemia), the investigator will indicate on the request form approval for dose escalation. The Data Management System will generate a unique kit number based on the randomized treatment assignment and the prior dose. If up-titration to the next dose is contraindicated, the Clinical Center investigator will indicate this on the study drug request form and a kit number corresponding to the current dose of SPL (or placebo) will be generated. At the end of the dose titration period, participants will be provided with a 6 week supply of study medication at the indicated dose. At the 12-week and 24-week visits, study drug request forms signed by the Clinical Center investigator will be submitted through the Data Management System to request 12 week supplies of study medication.

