5.5. Participant Adherence Monitoring

Study drug containers will be returned to site investigators at the conclusion of each 2-week period during dose escalation (weeks 2, 4 and 6), and at the Week 12, 24 and 36 visits. Pill counts will be performed to assess participant adherence with prescribed study medication.

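### The primary tolerability endpoint is not stated consistently for a 25 or 50 mg participant whose escalation is withheld for safety and who never reaches the assigned dose

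*Combined protocol and SAP*

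**What the plan says.** Tolerability is a primary outcome and is described in three places of the combined protocol and SAP.

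- Study Summary, Major Outcomes: "Tolerability: treatment adherence". No definition or threshold is attached.
- Section 2.1: "Tolerability events will include reduction in dose of study medication during the course of the treatment period or discontinuation of study drug".
- Section 3.2.1, first sentence: "Tolerability will be assessed on the basis of whether participants can continue the assigned dose throughout the entire treatment period". Second sentence: "Any reduction in dose of study medication will be considered a failure of primary tolerability".

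All participants on spironolactone start at 12.5 mg, so the 25 and 50 mg arms reach their assigned dose only by escalation (3.1, 5.2). Escalation can be withheld: "If up-titration to the next dose is contraindicated, the Clinical Center investigator will indicate this on the study drug request form", and a kit at the current dose is then issued (5.4). Down-titration is a separate request with its own scheme in 5.4. Someone who has not reached the assigned dose by Week 12 after considerable delay stays at the current dose to the end of the study (5.4).

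Adherence is measured in 5.5: "Pill counts will be performed to assess participant adherence with prescribed study medication". Section 5.4 adds: "All dose levels will be administered as a single capsule".

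**The concern.** Not being escalated is neither a reduction nor a discontinuation. A participant held below the assigned dose for safety therefore fails the criterion in the first sentence of 3.2.1 but triggers none of the events that 2.1 and 3.2.1 name. A programmer working from the listed events and one working from the first sentence would derive different endpoints.

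The difference is not spread evenly over the arms. The 50 mg arm has two real steps (weeks 2 and 4), the 25 mg arm has one, and the placebo and 12.5 mg arms have none. Coding by the listed events would make the two higher doses look better tolerated than they were and leave the other arms unchanged. Section 1.1 presents the trial as a source of data for choosing a dose, so the comparison most affected is the one the trial is meant to inform. If the rule is settled only after the data are seen, a primary outcome is in effect being defined post hoc.

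**Working it through.** The plan states no figure for tolerability, so there is none to reproduce. The check applies each wording to the same participant and then bounds the size.

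**1. Can a hold occur without a reduction?** Yes.

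- Potassium (6.9): a value of 6.0 to 6.9 mEq/L leads to a reduction only if the repeat is still at least 6.5, or still at least 6.0 with a dialysate bath of 2.0 mEq/L or lower. A repeat of at least 6.0 but below 6.5 on a higher bath meets neither condition, yet an investigator could reasonably withhold the next step.
- Hypotension (6.8): reducing study drug is fourth in the order of measures. It requires edema and, in addition, no other antihypertensive that could be stopped. Hypotension handled by the earlier measures can still be a reason not to escalate.

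**2. How is the participant coded?** Take someone assigned to 50 mg, held at 25 mg for safety, never escalated, with no later reduction or stop.

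| Text | Result |
|---|---|
| 3.2.1, first sentence | Failure: the assigned dose was never reached, so it was not continued |
| 3.1 | Points the same way: the step to 50 mg is conditional on having tolerated 25 mg |
| 3.2.1, second sentence | Not triggered: no reduction |
| 2.1 | No named event |
| Study Summary | Different measure: adherence, not defined there |

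**3. Does the analysis section settle it?** No. Section 7.4.1 covers the primary efficacy and safety outcomes. The as-treated rules in 7.3 assign dose for safety and efficacy analyses. Section 7 contains no tolerability analysis and no rule for participants who never reach the assigned dose.

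**4. How large can it be?** The allocation in 7.1 is 50 placebo and 25 per dose.

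- Participants who can be held below their assigned dose: 25 + 25 = 50 of 125. Not exposed: 50 + 25 = 75.
- One participant in a 25-person arm: 1/25 = 4 percentage points.

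The documents give no hold rate, so the counts below are assumptions. For one 25-person arm with no other failure, with exact (Clopper-Pearson) 95% intervals:

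| Held | Listed events | First sentence of 3.2.1 |
|---|---|---|
| 1 | 0% (0 to 13.7%) | 4% (0.1 to 20.4%) |
| 2 | 0% (0 to 13.7%) | 8% (1.0 to 26.0%) |
| 3 | 0% (0 to 13.7%) | 12% (2.5 to 31.2%) |

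With other failures present, let f be the share with a reduction or discontinuation, equal in all arms, and h the share held among the rest of the 25 and 50 mg arms. The failure rate in those two arms is f + h(1 − f). For f = 10%:

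- h = 10%: 0.10 + 0.10 × 0.90 = 19%
- h = 20%: 0.10 + 0.20 × 0.90 = 28%
- h = 30%: 0.10 + 0.30 × 0.90 = 37%

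Under the listed events the rate stays at 10%. The rate pooled over the three spironolactone arms becomes (2.5 + 9.5)/75 = 16%, (2.5 + 14.0)/75 = 22% and (2.5 + 18.5)/75 = 28%, while placebo stays at 10%.

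**The case against.** The strongest reply is that the text already leans one way. Section 3.2.1 is the endpoint section. Its first sentence can be read as the rule and its second as one certain instance of failure. The list in 2.1 is introduced as what events will include, so it need not be closed. Section 3.1 treats escalation as evidence of tolerance. All of this stands, and it is why failure is the better reading. It does not remove the gap: both places that name countable events omit this one, and nothing in section 7 tells the analyst to add it.

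Two stronger readings are tempting, and the documents support neither.

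- A reader might infer that the Study Summary gives the opposite coding, because a held participant who takes every capsule would pass a pill count. The label there is an undefined synopsis entry, and 5.5 never links pill counts to tolerability. It names a different measure; it does not code this participant a success.
- A reader might infer that one potassium result could leave one participant held at 25 mg, uncounted, while moving another from 50 to 25 mg, counted. The reduction criteria in 6.9 do not depend on the current dose, so a result that forces a reduction at 50 mg also forces one at 25 mg. The gap is confined to findings that block a step up but fall short of the rules in 6.8 and 6.9.

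It is also fair to say that the Week 12 rule in 5.4 follows an example of hospitalization and is not expressly tied to safety holds, so a permanent safety hold is partly inferred. Finally, 7.1 disclaims formal hypothesis testing, and no power figure depends on this point. Descriptive rates by dose are still the product, and they need a single definition.

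**Conclusion.** The concern holds in a limited form. For a 25 or 50 mg participant who is held for safety, does not meet the reduction rules and never reaches the assigned dose, the governing sentence of 3.2.1 gives a failure and the named events give none. Coding by the named events would understate intolerance in the 25 and 50 mg arms only.

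The ceiling is 50 of 125 participants, at 4 percentage points each in a 25-person arm. That ceiling is set by arm size and is not an estimate; the hold counts and the values of f and h are assumptions. With a few holds the shift lies well within the sampling uncertainty of a 25-person arm, but it runs in one direction and falls on the arms being compared for dose choice. It is worth correcting before analysis.

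**What to change.** 1. In 2.1 and 3.2.1 use one definition: tolerability failure is any dose reduction, discontinuation of study drug, or not reaching the assigned dose by Week 12 because of hyperkalemia, hypotension or another side effect. Report purely logistical non-attainment separately.
2. Change the Study Summary label to match, and report pill-count adherence as its own measure.
3. In 5.4 state that the Week 12 rule also applies to steps withheld for safety.
4. Report masked withheld steps by arm, including placebo and 12.5 mg. Only the 25 and 50 mg arms can fail by non-escalation, so the withheld-step rate in the other arms shows how often investigators hold when no dose change is at stake.

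The cost is wording edits and one extra table. The request form is completed at each 2-week interval in every arm and already records a contraindicated step, so no new visits, kits or samples are needed.

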3.2.2. Secondary Endpoints

Safety

- Serious hyperkalemia defined as hyperkalemia requiring hospitalization, emergency/unscheduled dialysis, or emergency/unscheduled resin therapy
- The combined incidence of potassium level >6.5 mEq/L or serious hyperkalemia defined as hyperkalemia requiring hospitalization, emergency/unscheduled dialysis, or emergency/unscheduled resin therapy
- Treatment-emergent events defined as the combined incidence of death, myocardial infarction, stroke hospitalization, potassium level >6.5 mEq/L, serious hyperkalemia, and serious hypotension
- The individual components of the treatment-emergent endpoint
- Cardiovascular death
- Hyperkalemia requiring adjustment in dialysate potassium or discontinuation of study medication
- Potassium ≥6.0 mEq/L
- Mean serum potassium during follow-up
- Proportion of dialysis sessions utilizing 1 mEq/L potassium dialysis solution bath
- Within-patient variability in serum potassium concentration

- Mean pre-dialysis blood pressure during follow-up
- Symptomatic inter- or recurrent intra-dialytic hypotension
 - Symptomatic inter-dialytic hypotension is defined as systolic blood pressure <90 mm Hg or hypotension requiring adjustment in blood pressure medications or treatment in an emergency or hospitalized setting
 - Recurrent intra-dialytic hypotension is defined as systolic blood pressure <80 mm Hg during ≥3 dialysis sessions per 30-day period or treatment for either hypotension or symptoms of hypotension during ≥3 dialysis sessions per 30-day period. Treatment includes saline infusion, lowering of the ultrafiltration rate or other interventions directed at hypotension such as vasopressor agents. Symptoms include but are not limited to muscle cramping, lightheadedness, and nausea.

Efficacy

Secondary outcome measures include other echocardiographic markers of systolic and diastolic function, circulating markers of fibrosis, heart rate variability and arrhythmias (sub-study), and coronary flow reserve (CFR) as assessed by myocardial positron emission tomography (PET)(sub-study).

- Change in left ventricular mass index (LVMI) between 0 and 36 weeks
- Change in ejection fraction between 0 and 36 weeks
- Change in myocardial strain and strain rate between 0 and 36 weeks
- Change in cardiac fibrosis markers between baseline and 36 weeks
- Change in inflammatory markers between baseline and 36 weeks
- Change in oxidative stress markers between baseline and 36 weeks
- Change in CFR between baseline and 36 weeks (sub-study)
- Association between change in CFR and change in E' (sub-study)
- Heart rate variability assessed by Medtronic SEEQ monitor (sub-study)
- Arrhythmias assessed by Medtronic SEEQ monitor (sub-study)

4. Participant Selection and Withdrawal

4.1. Inclusion Criteria

- a) Maintenance hemodialysis therapy for end-stage renal disease
- b) Age 18-85 years
- c) ≥3 calendar months since dialysis initiation
 - If a patient has been on dialysis for ≥3 but less than 6 calendar months, there must be:
 - i) no hospitalizations during the 6 weeks prior to screening and
 - ii) no change in EDW within 2 weeks of the screening date.
- d) For women of childbearing potential, willingness to use a highly effective method of birth control for up to 4 weeks after the last dose to study drug. See **Section 4.3.1** for definition of childbearing potential and acceptable methods of birth control.
- e) Ability to provide informed consent

4.2. Exclusion Criteria

- a) Serum potassium ≥ 6.5 mEq/L within the 3 months prior to screening
- b) Serum potassium level ≥ 6.0 mEq/L within 2 weeks prior to the baseline visit. If a potassium value is not available through routine clinical care during this 2-week period a potassium measurement will be performed as a research test.
- c) Unscheduled dialysis for hyperkalemia within the 3 months prior to screening
- d) Pre-dialysis systolic blood pressure <100 mm Hg within 2 weeks prior to screening or at the baseline visit
- e) 2 or more dialysis sessions within the month prior to screening with either 2 intra-dialytic measurements of systolic blood pressure <80 mm Hg
- f) Current dual use of ACEI and ARB
- g) Current use of digoxin
- h) Current use of spironolactone or eplerenone
- i) Allergy to spironolactone
- j) Inability to maintain dialysis machine blood flow ≥ 300 mL/min during any of the most recent 3 dialysis sessions prior to the screening visit as an indicator of vascular access dysfunction
- k) Mitral valve repair or replacement
- l) Severe mitral valve disease by echocardiography, coronary angiography or cardiac magnetic resonance imaging
- m) Anticipated kidney transplant, change to peritoneal dialysis, or transfer to another dialysis unit within 9 months
- n) Expected survival <9 months
- o) Pregnancy, anticipated pregnancy, or breastfeeding
- p) Incarceration
- q) Participation in another intervention study

